12.2.3 Data Management

Data Management will be coordinated by the Data Science of the sponsor in accordance with the SOPs for data management. All study-specific processes and definitions will be documented by Data Management. eCRF completion will be described in the eCRF instructions. Coding of medical terms and medications will be performed using MedDRA and World Health Organization Drug Dictionary, respectively.

12.2.4 Quality Assurance

The sponsor is implementing and maintaining quality assurance (QA) and QC systems with written SOPs to ensure that studies are conducted and data are generated, documented, recorded, and reported in compliance with the protocol, GCP and applicable regulatory requirement(s). Where applicable, the QA and QC systems and written SOPs of the CRO will be applied.

The sponsor or sponsor's designee may arrange to audit the study at any or all study sites and facilities. The audit may include on-site review of regulatory documents, CRFs and source documents. Direct access to these documents will be required by the auditors.

To support quality around subject safety and reliability of study results, quality tolerance limits (QTLs) are defined and monitored. QTLs represent the acceptable variation of study data, taking into consideration the current state of medical and statistical knowledge about the variables to be analyzed as well as the statistical design of the study. It is a level, point, or value associated with a parameter that should trigger an evaluation if a deviation is detected to determine if there is a possible systematic issue (i.e., a trend has occurred). The QTLs defined for this study, information regarding the QTL limit and limit justification, as well as associated activities are documented in STL-3458 QTL monitoring plan.

12.3 Contraception Requirements

WOCBP participants who choose complete abstinence must continue to have pregnancy tests, as specified in Schedule of Assessments.

WOMEN OF CHILDBEARING POTENTIAL DEFINITIONS AND METHODS OF CONTRACEPTION DEFINITIONS (WOCBP)

A woman is considered fertile following menarche and until becoming post-menopausal unless permanently sterile.

Women in the following categories are not considered WOCBP

- Premenarchal
- Premenopausal female with 1 of the following:
 - Documented hysterectomy
 - Documented bilateral salpingectomy
 - Documented bilateral oophorectomy
- Post-menopausal

Documentation of any of these categories can come from the site personnel's review of the female subject's medical records, medical examination, or medical history interview.

A postmenopausal state is defined as at least 12 months after last regular menstrual bleeding without an alternative medical cause.

- In case the last regular menstrual bleeding cannot be clearly determined, confirmation with repeated FSH measurements of at least > 40 IU/L (or higher per local institutional guidelines), is required.

Females on HRT and whose menopausal status is in doubt will be required to use one of the non-estrogen hormonal highly effective contraception methods if they wish to continue their HRT during the study. Otherwise, they must discontinue HRT to allow confirmation of postmenopausal status by repeated FSH measurements before study enrollment.

CONTRACEPTION GUIDANCE FOR FEMALE PARTICIPANTS OF CHILD BEARING POTENTIAL

One of the highly effective methods of contraception listed below is required at the time of informed consent and until the end of relevant systemic exposure, defined as 21 days after the final study drug administration.^a

Highly Effective Contraceptive Methods (Failure rate of < 1% per year when used consistently and correctly)^b

Combined (estrogen- and progestogen-containing) hormonal contraception associated with inhibition of ovulation^b

- oral
- intravaginal
- transdermal

Progestogen-only hormonal contraception associated with inhibition of ovulation

- oral
- injectable
- implantable

Hormonal methods of contraception containing a combination of estrogen and P4, vaginal ring, injectables, implants and intrauterine hormone-releasing systems

- intrauterine device
- bilateral tubal occlusion

^a Local laws and regulations may require use of alternative and/or additional contraception methods.

^b Typical use failure rates may differ from those when used consistently and correctly. Use should be consistent with local regulations regarding the use of contraceptive methods for participants participating in clinical studies.

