3.2 Inclusion Criteria

Subjects who meet all of the following criteria will be eligible to participate in the study:

1. Institutional Review Board (IRB)/Independent Ethics Committee (IEC) approved written informed consent and privacy language as per national regulations must be obtained from the subject or legally authorized representative prior to any study-related procedures.
2. Subject is born female, aged ≥ 40 years and ≤ 65 years of age at the screening visit.
3. Subject has a body mass index ≥ 18 kg/m² and ≤ 38 kg/m²
4. Subject must be seeking treatment or relief for VMS associated with menopause and confirmed as menopausal per 1 of the following criteria at the screening visit.
 - Spontaneous amenorrhea for ≥ 12 consecutive months
 - Spontaneous amenorrhea for ≥ 6 months with biochemical criteria of menopause (FSH > 40 IU/L), or

- Having had bilateral oophorectomy \geq 6 weeks prior to the screening visit.
5. Subject is seeking treatment for relief for VMS associated with menopause.
 6. Subject is in good general health as determined on the basis of medical history and general physical examination, including a bimanual clinical pelvic examination and clinical breast examination devoid of relevant clinical findings, performed at the screening visit; hematology and biochemistry parameters; pulse rate and/or blood pressure; and ECG within the reference range for the population studied, or showing no clinically relevant deviations, as judged by the investigator.
 7. Subject has documentation of a normal/negative or no clinically significant mammogram findings (obtained at screening or within the prior 12 months of trial enrollment). Appropriate documentation includes a written report or an electronic report indicating normal/negative or no clinically significant mammographic findings.
 8. Subject is willing to undergo a TVU to evaluate the uterus and ovaries at screening and at week 52 (EOT). For subjects who are withdrawn from the study prior to completion, a TVU should be collected at the ED visit.
 9. Subject is willing to undergo an endometrial biopsy at screening and at week 52 (EOT) or the ED visit for subjects who are withdrawn from the study prior to completion, and any time during the study in the case of uterine bleeding. The endometrial biopsy obtained at screening must be considered evaluable.

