3.3 Exclusion Criteria

Subjects who meet any of the following criteria will be excluded from participation in the study:

1. Subject uses a prohibited therapy (strong or moderate CYP1A2 inhibitors, HRT, hormonal contraceptive, any treatment for VMS [prescription, over the counter or herbal]) or is not willing to wash out and discontinue such drugs for the full extent of the study.

2. Subject has a known substance abuse or alcohol addiction within 6 months of screening, as assessed by investigator.
3. Subject has previous or current history of a malignant tumor, except for basal cell carcinoma.
4. Subject's systolic blood pressure is ≥ 130 mmHg or diastolic blood pressure is ≥ 80 mmHg based on the average of 2 to 3 readings on at least 2 different occasions within the screening period.
 - Subjects who do not meet the criteria may, at the discretion of the investigator, be re-assessed after initiation or review of antihypertensive measures.
 - Subjects with a medical history of hypertension can be enrolled at the discretion of the investigator once they are medically cleared (stable and compliant).
5. Subject has a history of severe allergy, hypersensitivity or intolerance to drugs in general, including the study drug and any of its excipients.
6. Subject has an unacceptable result from the TVU assessment at screening, i.e., full length of endometrial cavity cannot be visualized or presence of a clinically significant finding.
7. Subject has an endometrial biopsy confirming presence of disordered proliferative endometrium, endometrial hyperplasia, endometrial cancer or other clinically significant findings in the opinion of the investigator at screening.
8. Subject has a history within the last 6 months of undiagnosed uterine bleeding.
9. Subject has a history of seizures or other convulsive disorders.
10. Subject has a medical condition or chronic disease (including history of neurological [including cognitive], hepatic, renal, cardiovascular, gastrointestinal, pulmonary [e.g., moderate asthma], endocrine or gynecological disease) or malignancy that could confound interpretation of the study outcome in the opinion of the investigator.

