5.1.3.1 Previous Medication (Drugs and Therapies)

For women who recently discontinued hormone therapy, the therapy must have been discontinued for at least the following durations prior to the screening visit:

- 1 week or longer for prior vaginal hormonal products (rings, creams, gels, inserts);
- 4 weeks or longer for prior transdermal estrogen alone or estrogen/progestin products;
- 8 weeks or longer for prior oral estrogen and/or progestin therapy;
- 8 weeks or longer for prior intrauterine progestin therapy;

- 3 months or longer for prior progestin implants and estrogen alone injectable drug therapy; or
- 6 months or longer for prior estrogen pellet therapy or progestin injectable drug therapy.

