5.1.3.3 Prohibited Concomitant Medications

The following medications and therapies are prohibited throughout the study (from signing of informed consent through the last study-related activity):

- Use of hormonal medications such as hormone therapy, HRT or hormonal contraception or any treatment for VMS (prescription, over the counter or herbal).
- Investigational research products that have not been approved for any indication in the country where the subject is enrolled.
- Strong or moderate CYP1A2 inhibitors.

Refer to [Appendix 12.4 List of Excluded Concomitant Medications](#) for additional information.

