12.4 List of Excluded Concomitant Medications

These lists are not inclusive of all possible prohibited medications. In case of doubt, the Investigator must contact the local medical monitor.

- Use of hormonal medications such as hormone therapy, HRT or hormonal contraception or any treatment for menopausal symptoms (prescription, over the counter or herbal) is not allowed during the study.
- Investigational research products that have not been approved for any indication in the country where the subject is enrolled.

Strong CYP1A2 Inhibitors (AUCr > 5)	
Inhibitor	Therapeutic Class
Angelica root - Bai Zhi (Angelica dahurica radix)	Herbal Medications
ciprofloxacin	Antibiotics
clinafloxacin	Antibiotics
enoxacin	Antibiotics
fluvoxamine	SSRIs
oltipraz	Cancer Chemopreventive Agents
rofecoxib	NSAIDS
zafirlukast	Antiasthmatics
Moderate CYP1A2 Inhibitors (AUCr ≥ 2 and AUCr ≤ 5)	
Inhibitor	Therapeutic Class
3,4-methylene-dioxymethamphetamine (MDMA)	Recreational Drugs
etintidine	H-2 Receptor Antagonists
genistein	Food Products
idrocilamide	Muscle Relaxants
methoxsalen (8-methoxypsoralen)	Antipsoriatics
mexiletine	Antiarrhythmics
osilodrostat	Adrenal Steroidogenesis Inhibitors
oral contraceptives	Oral Contraceptives
phenylpropanolamine	Vasoconstrictors
pipemidic acid	Antibiotics
propafenone	Antiarrhythmics
propranolol	Alpha/Beta Adrenergic Antagonists
troleandomycin	Antibiotics
vemurafenib	Kinase Inhibitors

AUCr: area under the concentration-time curve ratio; CYP: cytochrome P450; MDMA: 3,4-methylene-dioxymethamphetamine; NSAID: nonsteroidal anti-inflammatory drugs; SSRI: Selective serotonin reuptake inhibitors.

Estrogen-Only Medicines	
Brand Name	Generic Name
Alora	Estradiol
Cenestin	Synthetic Conjugated Estrogens
Climara	Estradiol
Delestrogen	Estradiol Valerate
Divigel	Estradiol
Elestrin	Estradiol
Enjuvia	Synthetic Conjugated Estrogens
Esclim	Estradiol
Estrace	Estradiol
Estraderm	Estradiol
Estrasorb	Estradiol
Estring	Estradiol
EstroGel	Estradiol
Evamist	Estradiol
Femring	Estradiol Acetate
Femtrace	Estradiol Acetate
Menest	Esterified Estrogen
Menostar	Estradiol
(only used to prevent osteoporosis)	
Minivelle	Estradiol
Ogen	Estropipate
Ortho-Est	Estropipate
Premarin	Conjugated Estrogens
Vagifem	Estradiol
Vivelle	Estradiol
Vivelle-Dot	Estradiol
Progestin-Only Medicines	
Brand Name	Generic Name
Prometrium	Micronized Progesterone
Aygestin	norethindrone acetate
Provera	Medroxyprogesterone Acetate

Estrogen-Only Medicines	
Combination Estrogen and Progestin Medicines	

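### Appendix 12.3 requires women of childbearing potential to use a listed contraceptive, but 6 of its 8 bulleted methods are hormonal and banned elsewhere, and the follow-on pregnancy tests it cites are not in Table 1

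*Protocol*

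**What the plan says.** **The requirement.** Protocol Appendix 12.3 states that "One of the highly effective methods of contraception listed below is required at the time of informed consent" and continues the duty until 21 days after the final dose. Its list has three headings. The first two are combined and progestogen-only hormonal contraception. The third reads "Hormonal methods of contraception containing a combination of estrogen and P4, vaginal ring, injectables, implants and intrauterine hormone-releasing systems", and the intrauterine device and bilateral tubal occlusion are printed beneath it.

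**The ban.** Exclusion 1 in Section 3.3 removes a candidate if "Subject uses a prohibited therapy (strong or moderate CYP1A2 inhibitors, HRT, hormonal contraceptive, any treatment for VMS" applies to her, unless she is willing to wash out and stop for the whole study. Section 5.1.3.3 prohibits, from consent to the last study activity, "Use of hormonal medications such as hormone therapy, HRT or hormonal contraception or any treatment for VMS". Appendix 12.4 repeats the ban and also places oral contraceptives under "Moderate CYP1A2 Inhibitors (AUCr ≥ 2 and AUCr ≤ 5", a class that is prohibited in its own right.

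**Who counts as fertile.** Appendix 12.3 says: "A postmenopausal state is defined as at least 12 months after last regular menstrual bleeding". Criterion 4 in Section 3.2 also admits women with "Spontaneous amenorrhea for ≥ 6 months with biochemical criteria of menopause", the biochemical criterion being FSH above 40 IU/L.

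**Pregnancy tests.** Appendix 12.3 says that WOCBP who choose complete abstinence go on having pregnancy tests under the Schedule of Assessments. The urine pregnancy test row in Table 1 is marked once, at screening.

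**The concern.** Two parts of one protocol give opposite instructions. Sections 3.2 and 3.3 set no contraception requirement, so Appendix 12.3 is the only place that tells a site which methods to use. A woman who took up one of the hormonal options would either fail exclusion 1 or become a PD4 deviation (excluded concomitant treatment, Section 8.3). If she used an oral contraceptive, her exposure to a drug metabolized mainly by CYP1A2 (Section 1.3.2) could rise.

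The missing tests matter because pregnancy is a mandatory reason to stop treatment (Section 6.1) and the rat and rabbit studies showed litter loss (Section 1.4.1). As written, no scheduled test after screening would detect a pregnancy in a woman relying on abstinence.

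**Working it through.** No planned figure has to be reproduced. The check compares texts and makes two counts.

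**1. Count of listed methods (Appendix 12.3)**

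- Combined hormonal: oral, intravaginal, transdermal = 3, all banned.
- Progestogen-only: oral, injectable, implantable = 3, all banned.
- Under the third heading: intrauterine device, bilateral tubal occlusion = 2. Both can be used without hormones, although the heading above them is hormonal.

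Banned bullets: 6 of 8 = 75%. If the third heading is counted as one more hormonal entry: 7 of 9 = 78%.

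**2. Do the periods overlap?** The contraception duty runs from consent to 21 days after the last dose. The ban runs from consent to the last study activity, and the follow-up visit is 3 weeks (21 days) after the last dose. They cover essentially the same time.

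**3. Can an eligible woman be WOCBP under 12.3?**

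- Entry at 12 months or more of amenorrhea: postmenopausal under 12.3, so not affected.
- Entry after bilateral oophorectomy: exempt under 12.3.
- Entry at 6 to under 12 months with FSH above 40 IU/L: still fertile under 12.3 if she is less than 12 months from her last regular bleed and not sterile. Appendix 12.3 accepts FSH confirmation only where that date cannot be clearly determined, and then asks for repeated measurements. The entry FSH therefore does not settle the matter for a woman with a known date. Hysterectomy exempts no participant, because exclusion 20 bars it.

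So the list does apply to some eligible women.

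**4. Pregnancy tests after screening.** Table 1: 0. Inclusion 11 also refers to screening only. Table 3 (the crisis schedule) gives a local-laboratory alternative but points back to Table 1.

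**5. How many tests would a footnote add?** Let m be the months since the last regular bleed at screening and s the days from screening to day 1. Assume that WOCBP status ends at 12 months and that no regular bleed recurs.

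- Days remaining at screening = (12 − m) × 30.4375
- Study day on which status ends = days remaining − s + 1

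Nominal visit days, without visit 2b: 1, 29, 57, 85, 113, 141, 169. The values of s are 1, 35 (normal limit) and 50 (limit with a repeat biopsy).

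| m | Days remaining | Status ends on study day (s = 1 / 35 / 50) | Visits before then |
|---|---|---|---|
| 6 | 182.6 | 183 / 149 / 134 | 7 / 6 / 5 |
| 9 | 91.3 | 91 / 57 / 42 | 4 / 3 / 2 |
| 11 | 30.4 | before day 1 unless s is small; 30 at s = 1 | 2 / 0 / 0 |

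The most that a footnote would add is therefore about 5 to 7 urine tests, for a woman screened at exactly 6 months.

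**The case against.** The strongest reply is that harm is unlikely. A woman already on hormonal contraception is caught at screening by exclusion 1, for which no waiver is allowed. The ban is stated several times, subjects must consult before taking any medication (Section 5.1.3), and doubtful drugs go to the medical monitor (Appendix 12.4). Section 5.1.3.3 points sites to 12.4, and I found no pointer from the body of the protocol to 12.3. Section 5.4.3 allows unscheduled tests when clinically indicated. Surviving embryos in the animal studies showed no developmental effect. All of this stands and keeps the point minor. It does not reconcile the two texts, and permission for an unscheduled test is not the required testing that 12.3 cites.

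A reader might infer more than the documents support:

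- **That WOCBP cannot comply at all.** They can, with a non-hormonal intrauterine device or tubal occlusion.
- **That Section 5.1.3.1 is a further direct contradiction**, because it asks for "8 weeks or longer for prior intrauterine progestin therapy". Those washouts are written for women who recently stopped hormone therapy. Product types overlap, but the section is not a contraception rule, and the conflict does not need it.
- **That every WOCBP should be tested repeatedly.** Appendix 12.3 ties continued tests to those who choose abstinence.
- **That Section 5.2.2 already identifies the affected women.** It records the date of last menstruation, whereas 12.3 turns on the last regular bleed. The recorded date would include some women who are already postmenopausal under 12.3.
- **That fezolinetant exposure would rise 2- to 5-fold with an oral contraceptive.** That range defines the inhibitor class. The documents give no ratio for this pair.

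**Conclusion.** The conflict is real and lies in current text. Appendix 12.3 requires a method from a list of which 6 of 8 bullets are prohibited over the same period, and it cites continued pregnancy tests that Table 1 does not contain. It reaches only women who entered at 6 to under 12 months of amenorrhea, are less than 12 months from their last regular bleed and are not sterile. The documents do not give their number; that it is small is a judgment.

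The 5 to 7 test ceiling rests on an assumption. Appendix 12.3 describes no mid-study reassessment and states the contraception period as running to 21 days after the last dose. That a woman leaves WOCBP status at 12 months is a reasonable reading of its definition, not a stated rule.

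This is an optional but worthwhile safety and consistency correction, with no bearing on endpoints, analyses or sample size.

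**What to change.** 1. Restrict the Appendix 12.3 list to the non-hormonal intrauterine device and bilateral tubal occlusion, and drop the three hormonal headings.
2. Remove the option to continue HRT during the study, which exclusion 1 and Section 5.1.3.3 forbid. The sentence that follows it depends on it and asks for HRT to stop before enrollment, whereas Section 5.1.3.1 sets washouts of 1 week to 6 months before screening. Replace both with a statement that HRT must have stopped as Section 5.1.3.1 specifies.
3. Decide whether complete abstinence is accepted. If it is, say so and add a Table 1 footnote giving abstinent WOCBP a urine pregnancy test at existing visits while they remain WOCBP. If it is not, delete the sentence on continued tests.

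The cost is protocol wording and at most one footnote. If the footnote is chosen, sites must also establish the date of the last regular bleed for women admitted at 6 to under 12 months and track when their status changes. Under the assumption above, that adds about 5 to 7 tests at most per abstinent woman, at visits she already attends.

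### Protocol Appendix 12.3 offers hormonal contraceptives as accepted methods, although exclusion 1, section 5.1.3.3 and Appendix 12.4 prohibit them (minor)

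*Protocol*

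**What the plan says.** Protocol Appendix 12.3 sets a requirement for women of childbearing potential: "One of the highly effective methods of contraception listed below is required at the time of informed consent". It runs until 21 days after the last dose. The list that follows contains "Combined (estrogen- and progestogen-containing) hormonal contraception associated with inhibition of ovulation" (oral, intravaginal, transdermal), then progestogen-only methods (oral, injectable, implantable), then "Hormonal methods of contraception containing a combination of estrogen and P4, vaginal ring, injectables, implants and intrauterine hormone-releasing systems". The intrauterine device and bilateral tubal occlusion close the list. Complete abstinence is mentioned at the top of the appendix, but it is not a list entry.

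The prohibitions stand in three other places. Exclusion criterion 1 (section 3.3) opens with "Subject uses a prohibited therapy (strong or moderate CYP1A2 inhibitors, HRT, hormonal contraceptive" and also excludes women unwilling to wash out such drugs and stay off them for the whole study. Section 5.1.3.3 names HRT and hormonal contraception among therapies that are "prohibited throughout the study (from signing of informed consent through the last study-related activity"). Appendix 12.4 repeats the ban and also puts oral contraceptives in its table of moderate CYP1A2 inhibitors, a class prohibited in its own right.

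Appendix 12.3 also addresses women on HRT whose menopausal status is uncertain. It gives two branches: stay on HRT with a suitable contraceptive method, or stop HRT so that status can be confirmed before enrollment.

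**The concern.** A protocol should not require a choice from a list and forbid most of that list elsewhere. Appendix 12.3 carries no exception and no pointer to 5.1.3.3 or 12.4. Site staff who use it as their contraception guide would have to work out for themselves which entries are banned. If they did not, a participant could be directed to an estrogen or progestin in a trial whose primary items include endometrial hyperplasia and endometrial cancer (section 2.3.1), or to an oral contraceptive that the protocol itself lists as a CYP1A2 inhibitor. Either would be a major protocol deviation of type PD4 (section 8.3), brought about by following the protocol's own text.

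**Working it through.** No plan figure is involved, so the check sets the texts side by side.

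**Step 1. Do the two rules cover the same period?** The 12.3 requirement runs from consent to 21 days after the last dose. The ban runs from consent to the last study-related activity, and the follow-up visit falls about 3 weeks after the last dose: 3 × 7 = 21 days. Apart from the visit window of ± 3 days, the periods coincide. There is no stretch of time in which 12.3 could apply without the ban.

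**Step 2. Which listed methods survive the ban?**

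| Entry in 12.3 | Status under exclusion 1, 5.1.3.3 and 12.4 |
|---|---|
| Combined hormonal | Prohibited; the oral form is also a listed CYP1A2 inhibitor |
| Progestogen-only | Prohibited |
| Rings, injectables, implants, hormone-releasing systems | Prohibited |
| Intrauterine device | Compatible only if non-hormonal |
| Bilateral tubal occlusion | Compatible |

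Three of five entries are prohibited outright. One is compatible only on a condition that 12.3 does not state, and one is compatible. In the text as extracted, the last two entries sit directly beneath the hormonal heading. The layout may be broken there, and the restriction to a non-hormonal device is inferred from the bans.

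**Step 3. Can the 12.3 requirement reach any eligible woman?** Section 3.2, criterion 4, gives three routes to eligibility.

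- Amenorrhea of 12 months or more: the appendix says "A postmenopausal state is defined as at least 12 months after last regular menstrual bleeding without an alternative medical cause". Twelve months without any bleeding implies at least 12 months since regular bleeding, so these women normally fall outside the requirement.
- Bilateral oophorectomy: 12.3 places these women outside childbearing potential.
- "Spontaneous amenorrhea for ≥ 6 months with biochemical criteria of menopause (FSH > 40 IU/L"): a woman with 6 to under 12 months of amenorrhea can still be under 12 months from her last regular bleeding. She is then of childbearing potential under 12.3.

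Two things shrink the third group. The clocks differ: criterion 4 counts from any bleeding, 12.3 from the last regular bleeding, so a woman whose bleeding was irregular for some time may already have passed 12 months. There is also an FSH route: "In case the last regular menstrual bleeding cannot be clearly determined, confirmation with repeated FSH measurements of at least > 40 IU/L" can establish postmenopausal status. The group is not empty by definition, but the documents do not give its size.

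**Step 4. Does the HRT sentence conflict?** Its first branch treats continuing HRT during the study as a choice, and the second branch is worded as the alternative to it. Exclusion 1, 5.1.3.3 and 12.4 allow only the second. In practice the first branch is closed. Section 5.1.3.1 requires hormone therapy to have been stopped for set periods before screening. Criterion 4 requires confirmed menopause at screening, whereas the sentence is about women whose status is in doubt. Sections 3.2, 3.3 and 8.3 rule out waivers.

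**The case against.** The strongest reply is that no participant is likely to be affected. A woman already on a hormonal method is stopped by exclusion 1. Two of the three menopause routes need spontaneous amenorrhea, which is hard to establish in someone taking ovulation-suppressing hormones. What remains is a woman who starts a hormonal method after consent, despite the instruction in section 5.1.3 to consult site staff before taking any medication and despite a ban stated in several places. Both texts can also be satisfied together with a non-hormonal device or tubal occlusion, and 12.4 sends doubtful cases to the medical monitor.

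Most of this stands, and it is why the point is minor. It does not rescue the list. The medical monitor is consulted when there is doubt, and a method printed as acceptable may raise none. The objection also stands for the HRT sentence, which is residual wording.

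A reader might also infer that 12.3 promises repeated pregnancy tests that the Schedule fails to provide. The documents do not support this as a defect. The sentence on abstinent women defers to the Schedule of Assessments and sets no frequency of its own. Table 1 has one urine test, at screening, in line with inclusion criterion 11, and section 5.4.3 allows unscheduled tests when clinically indicated. The wording about continuing tests is loose and worth clarifying. Adding on-study tests would be a preference.

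**Conclusion.** Appendix 12.3 is wrong as written on hormonal contraception: it makes a choice from a list mandatory, and three of its five entries are prohibited by exclusion 1, 5.1.3.3 and 12.4. The HRT-continuation option contradicts the same bans but has essentially no operational reach. The severity is minor. The only women the contraceptive list can reach are some of those enrolled with 6 to under 12 months of amenorrhea and FSH above 40 IU/L. Calling that group small is a judgment, because the documents give no count.

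Because the trial has endometrial primary items and fezolinetant is metabolized mainly by CYP1A2, a reader might infer that the hyperplasia rate or the liver findings are at risk. Nothing in the documents supports that step: no hormone use is shown, the affected group is unquantified, and several controls stand in the way. No effect on any endpoint is claimed, and no sample size or error rate changes.

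**What to change.** In Appendix 12.3:

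- Delete the combined, progestogen-only and hormone-releasing methods.
- State that, from the list, only a non-hormonal intrauterine device or bilateral tubal occlusion is permitted.
- Say explicitly whether complete abstinence is also accepted. Deleting entries does not settle this, because abstinence is not on the list.
- Delete the option to continue HRT and keep only the requirement to stop it.
- Cross-reference sections 5.1.3.1 and 5.1.3.3 and Appendix 12.4.
- As a clarification only, reword the pregnancy-test sentence so that it plainly means the screening test in Table 1.

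The cost is wording in one appendix. No visit, assessment or analysis changes.
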